#### 7.3. Withdrawal

Study participation is voluntary and a subject may decide to withdraw their consent at any time with or without reason and without impact on their continued medical care.

A study Investigator may withdraw a subject form the study without the subject's consent. If this occurs, the Investigator will inform the subject. Reasons for subject withdrawal by an Investigator may include, but are not limited to:

- The Investigator decides it is in a subject's best interest not to continue participating in the study.
- The Investigator decides that it may be harmful for a subject to continue participating in the study.

- The subject is not compliant with study required follow-up.
- The study Sponsor (WAE Medical, Inc.) terminates the study early.
- The IRB, EC, or a regulatory agency decides to terminate the study early.
- The subject is considered lost-to-follow-up.

If a subject withdraws from the clinical study or if they are withdrawn by an Investigator, their status and reason for withdrawal will be documented on the applicable study CRF.

Subjects that withdraw or are withdrawn by the Investigator from the study after undergoing treatment with the study or control device will not be replaced for enrollment. Subjects who withdraw or are withdrawn from the study prior to undergoing treatment with the study or control device will be replaced for enrollment.

All applicable CRFs up to the point of withdrawal must be completed and will be used for analysis.

#### 7.4. Lost-to-Follow-up

In order to consider a subject lost-to-follow-up, site personnel should first make all reasonable efforts to locate and communicate with the subject. All attempts to contact the subject must be recorded in the subject's study file including the date, time and name of site personnel who have attempted to contact the subject. Subjects who are deemed lost-to-follow-up will not be replaced for enrollment and will be accounted for on the applicable study CRF.

All applicable CRFs up to the point of lost-to-follow-up status must be completed and will be used for analysis.

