## 7. Subject Accountability

#### 7.1. Point of Enrollment

Subjects may be enrolled in this study if they sign and date the informed consent form (ICF) and meet all of the selection criteria noted in Section 6 of this protocol. No study-related activity can take place until the subject is considered enrolled.

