#### 8.3. Screening (Within 10 Days of Index Procedure) (Hospital/Clinic Visit)

The Screening Visit may be performed at the same time as the Index Procedure. During the Screening Visit the following data collection and assessments will be performed:

- 1. Date of visit
- 2. Informed consent process
- 3. Inclusion/Exclusion criteria (refer to Section 6 of this protocol)
- 4. Enrollment (refer to Section 7 of this protocol)

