#### 9.4. Data Analyses

To assess whether the Primary Endpoint is met in each group of 15 subjects (as applicable), Criteria A-E must all pass receive a passing score. The questionnaire attached in Appendix A will be answer during each case to document performance of the Poseidon System relative to Criteria A-E

As defined above, criterion A will be assessed on a pass/fail basis. Only 1 failure in each group of 15 will be allowed; >1 failure will result in failure of criterion A.

Criteria B – E will be assessed using a Likert-scale. After 15 each criterion has been assessed in all subjects, scores will be compiled by calculating a mean Likert-score. To pass, each criterion must have a mean Likert score of >3. A score  $\leq$  3 is considered a failure. The rating of the Likert scale will be as follows:

- A value of 1 = Strongly Disagree
- A value of 2 = Disagree
- A value of 3 = Neutral
- A value of 4 =Agree
- A value of 5 = Strongly Agree

Secondary Endpoints will be analyzed as follows:

- 1. Safety: All adverse events will be collected and assessed for relationship to the study device and/or study procedure, seriousness, and severity. Adverse events will be grouped by type and presented in frequencies. If >2 device related SAEs occur, the endpoint will fail.
- 2. Overall Procedure Time: The mean of all procedure times will be taken. There are no pass/fail criteria for this endpoint.
- 3. Device Deficiencies: All device deficiencies will be collected, grouped by type, relationship to adverse events, and presented in frequencies. There are no pass/fail criteria for this endpoint.

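### Sections 7.3 and 7.4 give opposite replacement rules for a subject lost to follow-up before the procedure, so a group could be judged on fewer than 15 device uses

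*Combined protocol and SAP*

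**What the plan says.** Four parts of the protocol bear on this.

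- **Enrollment.** Section 7.1 ties it to consent and eligibility, not to device use: "Subjects may be enrolled in this study if they sign and date the informed consent form (ICF) and meet all of the selection criteria". Section 8.3 and Table 1 list enrollment as a screening item, and screening may be up to 10 days before the index procedure. It may also coincide with it: "The Screening Visit may be performed at the same time as the Index Procedure".
- **Withdrawal.** Section 7.3 gives this among the reasons for withdrawal by an investigator: "The subject is considered lost-to-follow-up". It then separates subjects by treatment. Those who leave after treatment are not replaced. For the others: "Subjects who withdraw or are withdrawn from the study prior to undergoing treatment with the study or control device will be replaced for enrollment".
- **Loss to follow-up.** Section 7.4 makes no such separation: "Subjects who are deemed lost-to-follow-up will not be replaced for enrollment and will be accounted for on the applicable study CRF".
- **Pass rule.** Section 9.4 states criterion A as a fixed count: "Only 1 failure in each group of 15 will be allowed; >1 failure will result in failure of criterion A". The safety endpoint in 9.4 is also a fixed count and fails when more than two device-related SAEs occur. Criteria B to E each require a mean Likert score above 3.

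**The concern.** One subject can fall under both rules. Someone who consents and qualifies at a separate screening visit, misses the colonoscopy and cannot be traced is lost to follow-up without having had the device. Section 7.3 requires a replacement and Section 7.4 forbids one. Section 7.2 does not settle it, because it replaces subjects found not to meet the selection criteria, and this subject met them.

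What is at stake is the denominator. Criteria A to E are recorded only at the index procedure, so an untreated subject who keeps a place contributes no device use. No section says what happens to the one-failure allowance or the SAE limit when a group has fewer than 15 uses. A pass in the first group ends the study with the device validated (Section 9.5), so the number of uses behind that pass should not depend on which of two adjacent sections a site applies.

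**Working it through.** **Step 1: the two rules side by side.**

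| Subject | Section 7.3 | Section 7.4 |
|---|---|---|
| Treated, then lost to follow-up | Not replaced | Not replaced |
| Enrolled, lost before treatment | Replaced | Not replaced |

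The sections agree in the first row and conflict in the second. Loss after treatment does not reduce the number of device uses. It affects only the two-week safety data.

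**Step 2: does the text say which rule prevails?** It does not. Section 8.9 lists withdrawal and loss to follow-up as separate ways of ending the study, which favors reading 7.4 as a rule of its own. Section 7.5 has the sponsor track progress toward 15 by enrollment, not by procedures performed.

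**Step 3: size of the effect on criterion A.** The plan has no operating characteristic to reproduce. The synopsis says that the study is not powered, and Section 9.3 bases the size on internal procedures. The stated rule is at most 1 failure in 15, a tolerated observed fraction of 1/15 = 6.7%. With 14 uses it becomes 1/14 = 7.1%.

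Assume independent cases with true failure rate p, which the documents do not give. For n device uses,

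P(pass A) = P(X ≤ 1) = (1 − p)^n + n·p·(1 − p)^(n − 1).

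- p = 10%, n = 15: 0.2059 + 0.3432 = 0.549
- p = 10%, n = 14: 0.2288 + 0.3559 = 0.585
- p = 20%, n = 15: 0.0352 + 0.1319 = 0.167
- p = 20%, n = 14: 0.0440 + 0.1539 = 0.198

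Over a wider range of assumed rates:

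| Uses n | p = 5% | 10% | 15% | 20% | 30% |
|---|---|---|---|---|---|
| 15 | 0.829 | 0.549 | 0.319 | 0.167 | 0.035 |
| 14 | 0.847 | 0.585 | 0.357 | 0.198 | 0.048 |
| 13 | 0.865 | 0.621 | 0.398 | 0.234 | 0.064 |
| 12 | 0.882 | 0.659 | 0.444 | 0.275 | 0.085 |

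The first missing use adds between about 1 and 4 percentage points. The documents give no no-show rate, so the rows for 13 and 12 only show the trend. The last would need 3 of 15 subjects (20%) to be untraceable before their procedure.

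With exactly one failure, the one-sided 95% Clopper-Pearson lower bound on the success rate is 72.1% for 15 uses and 70.3% for 14.

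**Step 4: the other rules.** The SAE limit is a fixed count, so fewer uses move it in the same direction. No event rate is given, and I put no figure on it. Criteria B to E are judged on means. Dropping a rating does not shift the expected mean, and if the true mean is above 3, a smaller n slightly lowers the chance of passing.

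**The case against.** The strongest reply is that follow-up in this protocol means the period after the procedure. Table 1 places only the two-week and unscheduled visits under that heading, and Section 5.1 describes subjects as followed after the procedure. On that reading, 7.4 concerns treated subjects who miss the two-week contact, and it agrees with 7.3. A pre-procedure no-show would then fall under 7.3 alone. This is plausible and may be what was meant. It does not fully resolve the matter, because 7.3 itself names loss to follow-up as a withdrawal reason and 7.4 carries no qualifier.

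Other text also points to 15 actual uses. Section 5.1 has the 15 subjects enroll and undergo the colonoscopy, and 9.4 refers to assessment in all subjects. These statements show intent, but they are not replacement rules.

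The case is narrow, and that stands. Same-day screening leaves almost no gap. Otherwise the subject must miss the procedure and remain unreachable after the efforts that 7.4 requires. The sponsor is told of each enrollment, so a shortfall could be noticed.

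A reader might infer that every untreated subject who holds a place makes validation easier to pass. The documents do not support that. It is true of the count rules only, and overall validation also requires criteria B to E, where a smaller group gives no systematic advantage. Nor can one infer that the 15-subject basis will be missed. The text permits a shortfall but does not make one likely.

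**Conclusion.** The conflict is in the current text and should be removed. For a subject enrolled at a separate screening visit and lost before the procedure, 7.3 and 7.4 give opposite instructions, and following 7.4 can leave a group short of 15 device uses with its count limits unchanged.

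The effect is modest. With one use missing, the chance of passing criterion A rises by 3.6 points (54.9% to 58.5%) at an assumed 10% failure rate, and by 3.1 points (16.7% to 19.8%) at 20%. These figures assume independent cases and failure rates that the documents do not state. The conclusion extends neither to criteria B to E nor to overall validation.

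**What to change.** Reword 7.4 along these lines: *A subject lost to follow-up after treatment with the study device is not replaced. A subject lost to follow-up before treatment is replaced, as Section 7.3 provides.*

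In 5.1 and 9.4, state that each group of 15 means 15 eligible subjects in whom use of the device was attempted, excluding screen failures under 7.2. That exclusion is needed because 7.2 allows a subject to screen out, and be replaced, as late as during the procedure.

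Define treatment identically in 7.3 and 7.4 as attempted use. Otherwise a failed placement in an eligible subject could be called untreated and replaced, which would remove a criterion A failure from the group.

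The cost is one reworded rule, a shared definition and a clause in each of two sections, best settled before enrollment begins. The sponsor may have to consent one further person for each pre-procedure loss, which 7.3 already requires. The intended number of device uses stays at 15 per group.

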#### 7.5. Enrollment Controls

8. The Sponsor will closely monitor enrollment for this study. Sites will be asked to notify the Sponsor regarding each new subject to be screened and enrolled. Sites will be notified when overall enrollment is close to reaching 15 and when enrollment is complete. If the Primary Endpoint and Secondary Endpoint 1 are not achieved, Sites and associated IRBs will be informed that device design changes will be made (which will take approximately 1-2 months). When it is time to begin enrollment of the second group of 15 subjects, sites and associated IRBs will be notified. Once again, the Sponsor will closely monitor enrollment and sites as was done with the first 15 subject.Study Methods

#### 8.1. Data Collection Schedule

Table 1.0 below provides a schedule of required study visits as well as assessments. Details regarding each study visit are provided in the following sections.

| Procedure/Assessment                        | Screening*
(≤10 Days of Index
Procedure) | Index Procedure
(0 Days) | Discharge | Follow-up Visits       |                      |
|---|--|-----------------------------|-----------|------------------------|----------------------|
|   |  |                             |           | 2 Weeks×
(± 7 Days) | Unscheduled
Visit |
| Informed Consent                            | X  |                             |           |                        |                      |
| Inclusion / Exclusion                       | X  |                             |           |                        |                      |
| Enrollment                                  | X  |                             |           |                        |                      |
| Demographics                                |  | X                           |           |                        |                      |
| Medical History                             |  | X                           |           |                        |                      |
| Device Information                          |  | X                           |           |                        |                      |
| Anesthesia Information                      |  | X                           |           |                        |                      |
| Acceptance Criteria for Design Validation   |  | X                           |           |                        |                      |
| Total Procedure Time (Scope-in / Scope-out) |  | X                           |           |                        |                      |
| Adverse Events                              |  | X                           | Х         | Х                      | X                    |
| Device Deficiencies                         |  | X                           |           |                        |                      |
| End of Study §                              |  |                             |           | Х                      |                      |

#### Table 1: Schedule of Required Visits and Assessments

\* May be combined with the Index Procedure Visit.

§ End of study is defined as completion of the 2-week Post Procedure Follow-up Visit, withdrawal, lost-to-follow-up, or death; whichever occurs first.

\*The 2 Week Post Procedure Follow-up Visit may be performed as a telephone all or in-hospital visit.

#### 8.2. Source Documentation

A source document is the first place where data is recorded for a clinical study. Source documents may include a subject's original medical record, source worksheets provided by the Sponsor for a specific clinical study, procedure and follow-up notes, clinical or office charts, imaging and imaging reports, etc. Source documents may be hard copy or electronic. All source documentation for this study must be maintained at the study site and made available for monitoring by the Sponsor and/or their representatives. Data from source documentation will be used by the clinical site to complete the CRFs for this study.

#### 8.3. Screening (Within 10 Days of Index Procedure) (Hospital/Clinic Visit)

The Screening Visit may be performed at the same time as the Index Procedure. During the Screening Visit the following data collection and assessments will be performed:

- 1. Date of visit
- 2. Informed consent process
- 3. Inclusion/Exclusion criteria (refer to Section 6 of this protocol)
- 4. Enrollment (refer to Section 7 of this protocol)

#### 8.3.1. Informed Consent Process

All subjects taking part in this clinical study must undergo the informed consent process. Subjects must be allowed adequate time to review the consent, raise questions, and make a voluntary decision to participate in the clinical study. Each subject must sign and date the IRB/EC approved ICF before any clinical study-related procedures are performed. A copy of signed ICF will be provided to the subject for his/her records. Study personnel should explain to the subject that even if the subject agrees to participate in the study and signs the ICF, during the procedure they demonstrate not to be a suitable candidate for the study and screen out.

#### 8.4. Index Procedure

#### 8.4.1. *Poseidon Procedure*

All enrolled subjects will undergo water-aided colonoscopy using the Poseidon System for fluid management. The operator of the Poseidon device must be a physician and must have received sufficient training in clinical endoscopic technique.

Investigators will assemble and place the Poseidon System prior to initiating colonoscopy according to the investigational instructions for use .

#### 8.4.2. Data Collection

During the Index Procedure Visit, the following data collection and assessments will be performed for both study arms:

- Date of Index Procedure
- Demographic information including:
  - Age at the time of the visit (years)
  - o Gender
  - o Height (cm)
  - Weight (kg)
  - o Race
  - Ethnicity
- Device information
- Type of anesthesia:
  - o MAC
  - o General
- Scope-in time (24 hour clock)
- Acceptance Criteria for Design Validation
- Scope-out time (24 hour clock)
- Adverse events
- Device deficiencies

#### 8.5. Immediate Post Procedure Visit

• Adverse events

#### 8.6. Discharge

At the point of Discharge the following data collection and assessments will be performed for both study arms:

• Date of discharge

#### 8.7. 2 Week Post Procedure Follow-up Visit (Telephone or Hospital) (+/- 3 day window)

The 2 Week Post Procedure may be performed over the phone or in the hospital. The following data will be collected during this visit:

- Date of Follow-up Visit
- Adverse events

#### 8.8. Unscheduled Visit

Unscheduled Visits are visits where study subjects are seen in person or over the phone between protocol required follow-up visits. If an Unscheduled Visit occurs the following data will be collected for both study arms:

- Date of Unscheduled Visit
- Reason for Unscheduled Visit
- Adverse events

#### 8.9. End of Study

End of study is defined as the completion of the 2-Week Post Procedure Follow-up Visit, withdrawal, lost-to-follow-up, or death; whichever occurs first. At this point, a subject's participation in the study will end.

# 9. Statistical Considerations

#### 9.1. Endpoints

#### 9.1.1. Primary Endpoint

The Primary Endpoint for this study is the assessment that the PoseidonTM System meets all acceptance criteria for design validation.

- f. User is able to operate device per the instructions for use. This criterion will be assessed in a pass/fail manner with an allowance of only 1 failure in the first 15 subjects and 1 failure in the second 15 subjects (if applicable).
- g. User shall not adversely influence typical actuation of a scope during colonoscopy procedure as assessed using a 5-point Likert scale.
- h. User assessment of functional acceptability of Poseidon device ratchet location as assessed using a 5-point Likert scale.
- i. User assessment of functional acceptability of Poseidon device intergluteal cleft fit as assessed using a 5-point Likert scale
- j. The Poseidon System shall minimize passage of fluids through and around the scope lumen when a scope is in the device, as assessed using a 5-point Likert scale.

To assess whether the Primary Endpoint is met in each group of 15 subjects (as applicable), Criteria A-E must all pass receive a passing score. The questionnaire attached in Appendix A will be answer during each case to document performance of the Poseidon System relative to Criteria A-E

As defined above, criterion A will be assessed on a pass/fail basis. Only 1 failure in each group of 15 will be allowed; >1 failure will result in failure of criterion A.

Criteria B – E will be assessed using a Likert-scale. After 15 each criterion has been assessed in all subjects, scores will be compiled by calculating a mean Likert-score. To pass, each criterion must have a mean Likert score of >3. A score  $\leq$  3 is considered a failure. The rating of the Likert scale will be as follows:

- A value of 1 = Strongly Disagree
- A value of 2 = Disagree
- A value of 3 = Neutral
- A value of 4 = Agree
- A value of 5 = Strongly Agree

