#### 9.2. General Statistical Methods

Descriptive statistics will be used to analyze the Primary and Secondary Endpoints. Data will be presented using means and standard deviations, median, quartiles, and minimum and maximum, as applicable.

Distributions of each continuous variable will be assessed prior to analysis and examined for normality. Data with interval or ratio scales to be analyzed that are not normally distributed will be analyzed using non-parametric statistics..

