#### 9.2.1. Number of Subjects per Investigative Site

If one clinical site is used for this study, it will enroll up to 30 subjects. If two clinical sites are used for this study an effort to have similar enrollment at each center will be made (i.e. 7 or 8 subjects at each site for each group of 15).

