#### 9.5. Passing Overall Validation

To pass overall validation in the first 15 subjects, the Primary Endpoint and Secondary Endpoint 1 must receive passing scores. If this is achieved in the first 15 subjects the Poseidon System has passed validation and the study is considered complete. If this is not achieved, design changes to the device are warranted.

Once the design changes are made, the new device will be tested in an additional 15 subjects. The Primary Endpoint and Secondary Endpoint 1 must receive passing scores. If this is achieved in the second 15 subjects, the Poseidon System has passed the validation. If this is not achieved in the second group of 15 subjects the Poseidon System has failed validation.

•

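### Is a pooled mean above Neutral too weak a pass rule for criteria B–E, given that it sets no limit on unfavourable ratings?

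*Combined protocol and SAP*

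**What the plan says.** Criteria B–E cover scope actuation, ratchet location, intergluteal cleft fit and fluid passage. Each is rated 1 (Strongly Disagree) to 5 (Strongly Agree) in every case. Section 9.4 says that "scores will be compiled by calculating a mean Likert-score", and section 9.1.1 sets the threshold: "To pass, each criterion must have a mean Likert score of >3". A mean of exactly 3 fails. The synopsis and section 4.1 give the same threshold. Only criterion A, operation according to the instructions for use, limits individual failures, at one per group of 15.

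The synopsis allows one or two sites. If two are used, section 9.2.1 aims at similar enrolment, that is "7 or 8 subjects at each site for each group of 15". Under section 9.5, if criteria A–E and Secondary Endpoint 1 all pass in the first group, "the Poseidon System has passed validation and the study is considered complete". If not, the device is redesigned and a second group of 15 is enrolled.

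On reporting, section 9.2 says: "Data will be presented using means and standard deviations, median, quartiles, and minimum and maximum, as applicable". The synopsis states that the study is not powered, and section 9.3 bases the sample size on the sponsor's internal validation procedures.

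**The concern.** A mean lets good scores cancel bad ones. With few cases and possibly very few users, the average can sit just above Neutral while a large share of cases, or a whole site, is unfavourable. Criterion E matters most, because it carries the study's only objective, fluid management. It could contribute to a validation pass although users at one of two sites disagreed in every case that the device minimised fluid passage. The contrast with criterion A, where a second failure in 15 is enough to fail, makes the absence of any limit for B–E look like an oversight. No reason is given for placing the cut-off at 3.

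**Working it through.** **Inputs from the plan.** Group size 15; pass if the mean exceeds 3 (sections 9.1.1 and 9.4); site shares of 7 and 8 if two sites are used (section 9.2.1). The plan gives no alpha, power, effect size or standard deviation, so there is no sample-size calculation to reproduce.

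**The rule as a sum.** A mean above 3 over 15 ratings means a sum above 45, so at least 46.

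| Pattern | Sum | Mean | Result |
|---|---|---|---|
| 7 Disagree + 8 Agree | 7×2 + 8×4 = 46 | 3.07 | pass |
| 8 Disagree + 7 Agree | 8×2 + 7×4 = 44 | 2.93 | fail |
| 9 Disagree + 6 Strongly Agree | 9×2 + 6×5 = 48 | 3.20 | pass |
| 10 Disagree + 5 Strongly Agree | 10×2 + 5×5 = 45 | 3.00 | fail |
| 14 Neutral + 1 Agree | 14×3 + 4 = 46 | 3.07 | pass |

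So up to 9 of 15 ratings can be unfavourable. The 7/8 site pattern passes at the minimum sum: changing one Agree to Neutral gives 45 and a fail.

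**What a cap would do.** The obvious candidate is to require also that at most 6 cases are rated 1 or 2, one fewer than the smaller site share. The probabilities below come from exact enumeration of 15 ratings. The distributions are assumptions (per cent rated 1/2/3/4/5), since the plan gives none.

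| Assumed ratings | Current rule | With cap of 6 |
|---|---|---|
| 8 cases 0/90/10/0/0, 7 cases 2/3/10/50/35 | 56% | 13% |
| 7 cases 0/90/10/0/0, 8 cases 2/3/10/50/35 | 82% | 38% |
| 8 cases all Disagree, 7 cases 2/3/10/50/35 | 43% | 0% |
| 7 cases all Disagree, 8 cases 2/3/10/50/35 | 75% | 0% |
| all 15 at 5/10/25/40/20, independent | 97.64% | 97.58% |
| all 15 at 10/20/40/20/10, independent | 45.3% | 45.2% |

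On these figures the cap looks strong and nearly free. Two further checks weaken it.

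*Uneven enrolment.* Section 9.2.1 promises an effort towards similar numbers, not an exact split. At 6/9, 6 Disagree + 9 Agree gives 6×2 + 9×4 = 48, mean 3.20, with 6 unfavourable ratings, so it passes with the cap too. If the other site follows 2/3/10/50/35, an all-Disagree site of 6 still passes 63% of the time under the cap, and a site of 5 passes 91% of the time. With a single site, the number 6 has no derivation.

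*Clustered ratings.* The worry about a split between sites supposes that ratings within a site are alike. The cost should be worked out on the same footing. Assuming a Dirichlet-multinomial model within sites of 8 and 7, for the 5/10/25/40/20 device:

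| Within-site correlation | Current rule | With cap of 6 | Cost (points) |
|---|---|---|---|
| 0.1 | 93.8% | 93.5% | 0.4 |
| 0.3 | 88.1% | 86.9% | 1.2 |
| 0.5 | 84.1% | 81.7% | 2.4 |
| 0.7 | 80.8% | 76.5% | 4.3 |

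(Costs are taken from unrounded values.) These are per criterion, four criteria must pass, and a failure leads to redesign and 15 more subjects.

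**Would the split be visible?** For 7 Disagree + 8 Agree the sum of squares is 7×4 + 8×16 = 156, so the variance is (156 − 46²/15)/14 = 1.07 and the standard deviation is 1.03. The minimum and lower quartile are both 2, and the median is 4. The summaries listed in section 9.2 would show the spread, though not which site it came from.

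**The case for a change.** The strongest case for a change is that, although unpowered, the study makes a binding decision. A rule that can declare validation with a majority of cases unfavourable says less than a reader will take it to say. The numerical counterexamples need no distributional assumption, and they hold with one site as well as two. The descriptive summaries do not enter the decision, and for the 7/8 pattern the median of 4 looks reassuring. Nor is every extra failure under a cap a loss: each would have at least 7 unfavourable ratings of 15, and a sponsor might want to fail such a device.

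All of that stands as a description of a lenient rule. It does not establish which stricter rule is right. A fixed cap of 6 depends on the 7/8 split and hardly touches a device whose ratings centre on Neutral. Requiring a mean above 3 at each site would answer the site worry directly. It would also fail more often than the pooled rule, because two site means above 3 imply a pooled mean above 3 but not the reverse. The extreme two-site scenario is hypothetical: nothing in the plan suggests opposite verdicts on the same device, and section 16.2 provides for training the investigators. A table of ratings by site and a sentence explaining the cut-off would be good reporting, but neither alters a pass or a fail.

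**Conclusion.** The concern reads the plan correctly, but no change is called for. Criteria B–E are lenient: up to 9 of 15 cases can be rated Disagree and a criterion still passes. A pass should be read for what it is, an average rating above Neutral. The threshold is prespecified, is the same wherever it appears, and breaks no stated figure. It also does not act alone, since criterion A, the other three Likert criteria and Secondary Endpoint 1 must all pass.

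Choosing a stricter threshold means balancing wrongly accepted against wrongly rejected devices, and the plan offers no basis for a particular balance. The cap examined here costs between about 0.05 and 4.3 percentage points per criterion for a moderately acceptable device, depending on clustering, and protects fully against an all-unfavourable site only at an exact 7/8 split. An analyst can count the ratings by category and site from the data already collected, without amending the plan.

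This rests on three assumptions: the rating distributions and within-site correlations are illustrative; the number of users is not stated; and Agree is the favourable answer on every questionnaire item, as the threshold implies (Appendix A is not in the text reviewed).
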